Medical history/current medical conditions						
Prior and concomitant medications	X	X	X	X	X	X
Signs and symptoms of severe malaria	S	S	S	S	S	S
Physical Examination	S	S	S	S	S	
Blood Pressure	X	X	X	X	X	X
Body Temperature 	X	X	X	X	X	X

Period	Follow-up					UNS
Visit Name	Day 5	Day 8	Day 15	Day 29	Day 43 / EOS	UNS
Days	5	8	15	29	43	1 to 43
Time (post-dose)	96h	168h	336h	672h	1008h	-
Body Height					X 	
Pulse rate	X	X	X	X	X	X
Body Weight					X	X
Clinical Chemistry 		X		X	X	X
Hematology 		X		X	X	X
Thyroid function 			X		X	
Urinalysis		X		X	X	X
Pregnancy test (Run-in Cohort only) 					X	
Blood sampling for parasite PCR genotyping 		X	X	X	X	X
Drug administration record						
Meal record						
PK sampling for patient ages 6 to <12 years in Cohort 1 dosed with KAF156/LUM-SDF QD for 2 days 		X				
PK sampling for patient ages 2 to <6 years in Cohort 1 and 6 months to <2 years in Cohort 2 dosed with KAF156/LUM-SDF QD for 2 days 		X				
PK sampling for patients dosed with Coartem ®		X				
Electrocardiogram (ECG) for patients dosed with KAF156/LUM-SDF QD for 2 days		X			X	
Electrocardiogram (ECG) for patients dosed with Coartem ®		X			X	
Overnight Hospital Stay						

 Fever monitoring will be done every 6 hours until resolution of fever, defined as being afebrile for 24 hours.

 Cohorts 1 and 2: Comparator only (Coartem®). Coartem® will be given at 0, 8, 24, 36, 48 and 60 hours. For all drug administrations actual time should be recorded.

 The number of samples/blood draws and total blood volume collected will remain under the limits recommended in this population (Howie 2011).

 PCR will be used for genotyping to establish malaria recrudescence/reinfection. . At screening, blood

Period	Follow-up					UNS
Visit Name	Day 5	Day 8	Day 15	Day 29	Day 43 / EOS	UNS
Days	5	8	15	29	43	1 to 43
Time (post-dose)	96h	168h	336h	672h	1008h	-

sample will be collected in all patients fulfilling eligibility criteria for inclusion in the study. A second blood sample collected as per Table above will be analyzed only in patients showing treatment failure before standard-of-care is administered.

 Also applies to any repeats

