 - d. had a recrudescence if parasitaemia is present from Day 8 to Day 29, or
 - e. had a new infection at Day 29 visit or later

Food noncompliance in the Run-in cohort is considered as important PD. Important protocol deviations for exclusion from PPS are specified in [Table 5-14](#) and will be identified by the clinical team before the database lock.

PK analysis set

Run-in Cohort

PK Analysis set: All the subjects in the safety analysis set who have at least one evaluable PK concentration. A profile is considered evaluable for that period if following conditions are satisfied:

- Participants took at least 80% dosages of randomized study medication
- If a patient vomited the original dose but did not vomit the replacement dose
- Participants with no protocol deviations (PD) that may have an impact on the PK data

PK analysis set-partial food compliance: all subjects in the PK analysis set who are compliant to meal criteria (within 30 minutes of drug administration and took at least 70% of the standard meal) on any of the two dosing days.

PK analysis set-Full food compliance: all subjects in the PK analysis set who are compliant to meal criteria (within 30 minutes of drug administration and took at least 70% of the standard meal) on both dosing days.

Note that meal non-compliance for the run-in cohorts is identified using the PD (protocol deviation) code OTH04.

Cohort 1 and Cohort 2

PK Analysis set: All the subjects in the safety analysis set who have at least one evaluable PK concentration. A profile is considered evaluable for that period if following conditions are satisfied:

- Participants took at least 80% dosages of randomized study medication
- If a patient vomited the original dose but did not vomit the replacement dose
- Participants with no protocol deviations (PD) that may have an impact on the PK data

PK analysis set-partial food compliance*: all subjects in the PK analysis set who are compliant to meal criteria (within 1 hour (± 5 min) of drug administration and took at least 70% of light meal) on both Days 2 and 3.

PK analysis set-Full food compliance*: All subjects in the PK analysis set who are compliant to meal criteria (within 1 hour (± 5 min) of drug administration and took at least 70% of light meal) on all three dosing days.

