After about 24 patients have been randomized in Cohort 2, PK checking along with safety and efficacy will be evaluated to see if the dose level of KAF156 and/or LUM-SDF is appropriate for this age group. Since lower lumefantrine concentration at 168 hours is associated with higher recrudescence in Coartem[®] ([WWARN Lumefantrine PK/PD Study Group, 2015](#)), lumefantrine concentration at 168 hours will be the key PK parameter to be checked. Difference in lumefantrine concentration at 168 hours between the 2 treatment groups (KAF156 and LUM-SDF combination divided by Coartem[®]) will be evaluated using the geometric mean ratio and its 90% confidence interval between the 2 groups. In the KAF156A2202 Part A, the SD of log lumefantrine concentration at 168 hours was 0.63 and 0.51 for KAF156 400 mg/LUM-SDF 960 mg QDx2 group and Coartem[®], respectively. Therefore, it's assumed that the common SD for KAF156 and LUM-SDF combination and Coartem[®] in this study is 0.57 (average of 0.63 and 0.51). Assuming that there is no difference in lumefantrine concentration at 168 hours between the two treatment groups, a sample size of 10 patients per group will provide 80% power to reject the null hypothesis that the lumefantrine concentration at 168 hours is at least 50% lower in the KAF156 and LUM-SDF group than in the Coartem[®] group at 1-sided alpha of 5% (nQuery 8.4 Module MTE0-1/Two Group t-test of Non-Inferiority in Means). To adjust for potential non-evaluable lumefantrine concentration at 168 hours, the PK checking will be performed after approximately 24 patients have been randomized and reached the visit at Day 8.

Power consideration for safety (QTcF effect) in the first 24 patients in Run-in Cohort

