5.1.4 Visit windows

When visit windows are used, all visits will be re-aligned, i.e., they will be mapped into one of the visit windows. E.g., if the Day 4 visit of a patient is delayed and occurs on Day 7, say, it will be re-aligned to visit window Day 8. In the case of major deviations from the visit schedule, or due to unscheduled visits, several assessments of a patient may fall in a particular visit window (either scheduled or unscheduled). Statistical approaches to handle multiple assessments in a given visit window are specified below.

- Of note, patients are allowed to have gaps in visits. All data collected will be displayed in listings.
- Lower limit and upper limit of the Day 29 visit is set to be Day 27 and Day 33 respectively, with narrow window since this is the primary analysis timepoint.
- The following rules are used to determine the window for other visits post baseline:
 - “Lower limit” = “upper limit of prior applicable visit” + 1.
 - “Upper limit” = “target day of current visit” + integer part of (“target day of next applicable visit” – “target day of current visit”)/2 with the exception of Day 29
 - No upper limit for Day 43 visit
 - Upper limit of Day 15 is one day before the lower limit of Day 29

For assessments that are scheduled to be performed only once on a day, [Table 5-5](#) describes the analysis windows mapping to visits (not just scheduled visits) based on study days alone. For the assessments that may be performed on multiple timepoints on a day, [Table 5-6](#) describes the analysis windows mapping to visits based on study day and time. Repeat and/or unscheduled visits (which will be numbered in the database according to new NCDS standards) will be mapped for analysis purposes in the same way. If there are multiple measurements within an analysis window, the conventions defined in [Table 5-7](#) will be used to determine the appropriate measurement to be selected for analysis.

The mapped visits will be used in the by visit analyses. However, the listings will show all collected data regardless of used in the by visit analyses.

Table 5-5 Analysis visit windows based on study days alone

Analysis Visit	Target Day	Analysis window for assessment group		
		Vital signs/ Chemistry/ Hematology/ Urinalysis	Thyroid function	
Baseline	1	Up to Day 1	Up to Day 1	
Day 2	2	Day 2	NA	
Day 3	3	Day 3	NA	
Day 4	4	Day 4	NA	
Day 5	5	Day 5 - 6	NA	
Day 8	8	Day 7 - 11	NA	
Day 15	15	Day 12 - 26	Day 2 - 29	
Day 29	29	Day 27 - 33	NA	

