Day 43/End of study	43	Day 34 and above	Day 30 and above	

Table 5-6 Analysis visit windows based on study day and time

Analysis Visit	Analysis timepoint	Analysis window for assessment group			
		Parasite count/Temperature*	ECG	PK (Run-in)	PK (Cohorts 1&2)
Baseline	0 hrs	up to 0 hrs	up to 0 hrs	up to 0 hrs	up to 0 hrs
Day 1	1 hrs	NA	NA	> 0 - 2 hrs	NA
	3 hrs	NA	>0 – 4.5 hrs	> 2 – 3.5 hrs	>0 – 4.5 hrs
	4 hrs	NA	NA	>3.5 – 4.5 hrs	NA
	5 hrs	NA	NA	>4.5 – 5.5 hrs	NA
	6 hrs	>0 - 9 hrs	>4.5 - 15 hrs	>5.5 - 7 hrs	>4.5 – 15 hrs
	8 hrs	NA	NA	>7 – 16 hrs	NA
	12 hrs	>9 - 18 hrs	NA	NA	NA
Day 2	24 hrs	>18 hrs to 33 hrs	>15 – 25.5 hrs	>16 – 24.5 hrs	>15 – 25.5 hrs
	25 hrs	NA	NA	>24.5 – 26 hrs	NA
	27 hrs	NA	>25.5 – 28.5 hrs	>26 - 27.5 hrs	>25.5 – 28.5 hrs
	28 hrs	NA	NA	>27.5 – 28.5 hrs	NA
	29 hrs	NA	NA	>28.5 – 29.5 hrs	NA
	30 hrs	NA	>28.5 - 39 hrs	>29.5 - 31 hrs	>28.5 – 39 hrs
	32 hrs	NA	NA	>31 - 40 hrs	NA
	36 hrs	>33 – 42 hrs	NA	NA	NA
Day 3	48 hrs	>42 – 60 hrs	>39 – 49.5 hrs	>40 – 60 hrs	>39 – 60 hrs
Day 4	51 hrs	NA	>49.5 - 52.5 hrs	NA	>49.5 - 52.5 hrs
	54 hrs	NA	>52.5 – 61 hrs	NA	>52.5 – 61 hrs
	68 hrs	NA	>61 – 70 hrs	NA	>61 – 70 hrs
	72 hrs	>60 hrs to Day 4	>70 hrs to Day 5	>60 – 120 hrs	> 60 hrs
Day 5	NA	Day 5 - 6	NA	NA	NA
Day 8	168 hrs	Day 7 – 11	Day 6 -25	>120 hrs	NA

Day 15	NA	Day 12 - 26	NA	NA	NA
Day 29	NA	Day 27 - 33	NA	NA	NA
Day 43/End of study	NA	Day 34 and above	Day 26 and above	NA	NA

*Temperature should be checked every 6 hours until no fever. Since temperature is used for treatment failure also, the same window of parasite count is used.

Table 5-7 Rules for flagging variables

Timing of measurement	Type of data	Rule
Baseline	All data	The last measurement made prior to administration of the first dose of study treatment – note this may include measurements taken on the day of randomization. If a patient did not receive any dose of study treatment, then the randomization date will be used.
Post-baseline efficacy	parasite count and temperature	The measurement closest to the target day/time will be used. In the event two measurements are taken equally apart, the first one will be used.

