		
parasites cleared prior to the positive blood smear parasite
 
 Not classified as non-responder before Day 8, no positive blood smear parasite before Day 29, blood smear parasite result is missing at Day 29, and blood smear parasite result is not negative or new infection at Day 43
SAF	NA	
 Not in Randomized set No study drug taken
PK	
 Patients who received concomitant prohibited medication which may have an impact on PK exposure 	
 Not in SAF No evaluable pharmacokinetic parameter data Compliance is <100% of randomized study medication taken

6 Reference

Stepniewska K and White NJ (2006) Some considerations in the design and interpretation of antimalarial drug trials in uncomplicated falciparum malaria. *Malaria Journal*; 5:127.

Collett, D. (1994), *Modeling Survival Data in Medical Research*, London: Chapman & Hall.

SAS/STAT ® 9.1 User's Guide. Cary, NC: SAS Institute Inc.

Brookmeyer, R. and Crowley, J. (1982) A confidence interval for the median survival time. *Biometrics*, 38, 29-41. doi:10.2307/2530286

Fourth Report on Diagnosis, Evaluation and Treatment of High Blood Pressure in Children and Adolescents. *Pediatrics* 2004; 114; 555 (see section 5.5.1 for detailed computation)

BMI-for-age percentiles categories (P3, P5, P10, P25, P50, P75, P85, P90, P95, P97) are obtained from the WHO Growth Charts (<http://www.who.int/childgrowth/en/>)

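### SAP Table 5-6 gives Cohorts 1 and 2 no 168-hour PK window and has overlapping 48 to 72 hour windows; separately, the PK set has two compliance cut-offs, 80% and 100%

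*SAP*

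**What the plan says.** **Windows.** SAP 5.1.4 says of visit windows that, when they are used, "all visits will be re-aligned, i.e., they will be mapped into one of the visit windows", and adds: "The mapped visits will be used in the by visit analyses". Table 5-6 has one PK column for the Run-in Cohort and one for Cohorts 1 and 2. The 168 h row reads "Day 8 168 hrs Day 7 – 11 Day 6 -25 >120 hrs NA" and the 72 h row reads "72 hrs >60 hrs to Day 4 >70 hrs to Day 5 >60 – 120 hrs > 60 hrs"; in both, the last two cells are Run-in PK and then Cohorts 1 and 2 PK. The Cohorts 1 and 2 column also gives 48 h as above 39 to 60 h, 51 h as above 49.5 to 52.5 h, 54 h as above 52.5 to 61 h, and 68 h as above 61 to 70 h.

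**Sampling.** Protocol Table 8-2 marks Day 8 (168 h) in the row "PK sampling for patient ages 2 to <6 years in Cohort 1 and 6 months to <2 years in Cohort 2 dosed with" the 2-day regimen, in the row for ages 6 to under 12 years, and in the Coartem row.

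**Role of the 168 h value.** SAP Table 1-2 lists it among the secondary PK endpoints for the younger cohorts. For the check after about 24 patients in Cohort 2, SAP 3.1.2 states that "lumefantrine concentration at 168 hours will be the key PK parameter to be checked". Protocol Table 12-1 defines C168 by the scheduled 168 h time point, and SAP 2.9 reports concentrations at nominal times, 168 h included.

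**PK set.** SAP 2.2 requires for both parts of the study: "Participants took at least 80% dosages of randomized study medication". Protocol 12.1 also says at least 80%. The PK row of SAP Table 5-14 excludes a patient if "Compliance is <100% of randomized study medication taken". SAP Section 4 declares no change to the protocol's analyses.

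**The concern.** The table that labels PK samples by visit has no place for the Day 8 sample in Cohorts 1 and 2, so that sample takes the label of a time point four days earlier. The overlaps mean that 51, 54 and 68 h samples each fit two windows. In the 3-day regimen the 48 h sample is taken before the third KAF156/LUM-SDF dose, and the 51 h and 54 h samples after it, so pre-dose and post-dose values can share the 48 h label.

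The effect differs by arm. Coartem PK sampling is at 24, 48 and 68 h and Day 8, with no 72 h sample, whereas KAF156/LUM-SDF is sampled at 72 h. A by-visit row for 72 h could therefore set a KAF156/LUM-SDF 72 h value beside a Coartem 68 h or 168 h value.

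The two compliance cut-offs define two different PK populations, and nothing says which governs.

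**Working it through.** **1. Mapping sampling times through the Cohorts 1 and 2 column.** A time h belongs to a window (l, u] when l < h ≤ u; the 72 h window is h > 60. Protocol Tables 8-2 and 8-3 allow ±2 h from 24 to 72 h and ±24 h beyond 72 h, so a Day 8 sample may lie between 168 − 24 = 144 h and 168 + 24 = 192 h.

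| Sample time (h) | Windows it falls in, Cohorts 1 and 2 |
|---|---|
| 48 | 48 |
| 51 | 48 and 51 |
| 54 | 48 and 54 |
| 60.5 | 54 and 72 |
| 68 | 68 and 72 |
| 72 | 72 |
| 144, 168, 192 | 72 only |

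Under the Run-in limits (72 h: above 60 to 120 h; 168 h: above 120 h), 144, 168 and 192 h all map to 168 h.

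**2. Is the NA an artefact of text extraction?** It does not look like one. The 168 h row has all its cells, and an open-ended 72 h cell is what one would expect if no later window existed. The ECG column has non-overlapping limits for the same rows (48 h ends at 49.5 h, 72 h starts above 70 h). In the PK column, 48 h ends and 72 h begins at exactly 60 h. That fits the SAP's change record, which shows 51, 54 and 68 h being added to the table; the neighbouring PK limits were probably not updated.

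**3. Compliance.** SAP 2.4.1 computes compliance per drug as full doses taken over planned doses, and averages the two drugs for the combination.
- The SAP's own example: (75% + 100%)/2 = 87.5%.
- A Coartem patient with 5 of 6 doses: 5/6 = 83.3%.
- A 3-day combination patient missing one dose of one drug: (66.7% + 100%)/2 = 83.3%.

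All three are kept by the 80% rule and removed by the 100% rule.

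**4. The planned size of the Cohort 2 check.** Inputs from SAP 3.1.2: margin ratio 0.5, so ln 2 = 0.693 on the log scale; SD 0.57; true difference 0; one-sided 5%; 10 per group for 80% power. For a two-group t-test the noncentrality is 0.693/(0.57 × √(2/n)), with 2n − 2 degrees of freedom.
- n = 10: 0.693/(0.57 × 0.4472) = 2.72; power 83.4%.
- n = 9: 0.693/(0.57 × 0.4714) = 2.58; power 79.5%.

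Ten is the smallest number per group with at least 80% power, so the plan's figure reproduces. It depends on neither the windows nor the cut-off.

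**The case against.** The strongest reply is that C168 does not need the window. Protocol Table 12-1 ties it to the scheduled time point, SAP 2.9 reports nominal times including 168 h, the data monitoring committee outputs name a 168 h concentration, and the SAP 2.10 scatter plot names Day 8 concentrations. The window text applies only when windows are used, and listings keep all data. This stands, and it limits the damage to analyses that use mapped visits. It does not remove the conflict: the SAP has two rules for the same sample and does not say which governs.

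Four stronger readings are tempting, and the documents do not support them.
- *The 168 h sample would certainly be discarded for the closer 72 h one.* The closest-to-target rule in Table 5-7 is written for parasite count, temperature and safety data; there is no PK rule. Coartem also has no scheduled 72 h sample to displace it.
- *Late exposure would be overstated.* If concentrations decline after the last dose, a 168 h value labelled 72 h lowers the 72 h summary. The documents give no concentrations from which to size this.
- *The 100% rule would materially cut the power of the Cohort 2 check.* Nothing in the documents says how many patients it would remove. Dosing is supervised in hospital, and a vomited dose successfully replaced counts as taken, so compliance below 100% should be uncommon.
- *The 168 h concentration is the key PK parameter of the whole study.* The SAP uses that wording only for the Cohort 2 check.

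The extracted follow-up part of Protocol Table 8-3 shows no PK row, which might suggest that NA is right for the 3-day regimen. The ECG rows are missing there too, so lost text is the likelier explanation, and the endpoint list and SAP 2.9 still call for a 168 h value.

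**Conclusion.** The concern holds as two specification errors. First, Table 5-6 followed as written labels every Day 8 PK sample in Cohorts 1 and 2 as 72 h wherever mapped visits are used, and lets 51, 54 and 68 h samples each fall in two windows. Second, the PK set has contradictory cut-offs, 80% in SAP 2.2 and Protocol 12.1 against 100% in Table 5-14, although the SAP declares no departure from the protocol.

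The mapping is exact given the table. The effect on reported concentrations cannot be computed from the documents, nor can the number of patients between 80% and 100% compliance. The per-protocol set, the non-inferiority test and the planned 10 per group are untouched. At stake is whether a secondary PK endpoint and its population are uniquely defined; they should be before database lock.

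**What to change.** 1. In the Cohorts 1 and 2 PK column, add a 168 h window above 120 h and cap the 72 h window at 120 h, as in the Run-in column.
2. Make the 48, 51, 54, 68 and 72 h windows non-overlapping, and assign scheduled samples by nominal time. Copying the ECG limits would not be enough. With 48 h ending at 49.5 h, a 48 h sample taken at 50 h, within the ±2 h tolerance, would move to 51 h. With 68 h ending at 70 h, a KAF156/LUM-SDF 72 h sample taken at 70 h would move to 68 h, a Coartem-only PK time. Defining windows by arm and regimen separates 68 h from 72 h. In the 3-day regimen the tolerances of 48 h (46 to 50 h) and 51 h (49 to 53 h) themselves overlap, so nominal time is the cleaner rule there.
3. State that C168 uses the scheduled 168 h sample, in line with Protocol Table 12-1 and SAP 2.9.
4. Change the Table 5-14 PK exclusion to below 80%, to match SAP 2.2 and Protocol 12.1.

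The cost is a SAP table edit and limited reprogramming of the PK visit derivation and the PK set flag. No new data and no change in sample size are needed.

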5.2 Non-study drug antimalarials

Table 5-8 Table of non-study drug antimalarials with respective ATC codes

Non-study drug antimalarials	ATC code	ATC name
Aminoquinolines	P01BA01	Chloroquine
	P01BA02	Hydroxychloroquine
	P01BA03	Primaquine
	P01BA06	Amodiaquine
Biguanides	P01BB01	Proguanil
	P01BB02	Cycloguanil embonate
	P01BB51	Proguanil, combinations
Methanolquinoline	P01BC01	Quinine
	P01BC02	Mefloquine
Diaminopyrimidines	P01BD01	Pyrimethamine
	P01BD51	Pyrimethamine, combinations
Artemisinin and derivatives, plain	P01BE01	Artemisinin
	P01BE02	Artemether
	P01BE03	Artesunate
	P01BE04	Artemotil
	P01BE05	Artenimol
Artemisinin and derivatives, combinations	P01BF02	Artesunate and mefloquine
	P01BF03	Artesunate and amodiaquine
	P01BF04	Artesunate, sulphamethopyrazine and pyrimethamine
	P01BF05	Artenimol and piperazine
	P01BF06	Artesunate and pyronaridine
	P01BX01	Halofantrine
Other Antimalarials		

Coartem*

P01BX02

Arterolane and Piperaquine

P01BF01

Artemether and lumefantrine

*in case used by patients receiving KAF156/Lum-SDF

5.3 Prohibited medications

Table 5-9 Table of prohibited medication with respective ATC codes

Category	General classification	ATC code	Product name
Drug-drug interaction	ANALGESICS	N02CC06	Eletriptan
		N02CA01	Dihydroergotamine
		N02CA02	Ergotamine
	ANESTHETICS	N02AB03	Fentanyl
		N01AH02	Alfentanil
		N01AH01	Fentanyl
	ANTIARRHYTHMICS	C01BD07	Dronedarone
		C01BC04	Flecainide
		C01BA01	Quinidine
		N06AA01	Desipramine
		N06AX16	Venlafaxine
		N06AX12	Bupropion
		N06AA02	Imipramine
		N06AA09	Amitriptyline
		N06AA04	Clomipramine
	ANTIEMETICS AND ANTINAUSEANTS	A04AD12	Aprepitant
		N03AB02	Phenytoin
	ANTIEPILEPTICS	R06AX11	Astemizole
		R06AX12	Terfenadine
		R06AX13	Loratadine
	ANTIHISTAMINES FOR SYSTEMIC USE	M01AH01	Celecoxib
		L01CD01	Paclitaxel
	ANTIINFLAMMATORY AND ANTIRHEUMATIC PRODUCTS	N05AB03	Perphenazine
	ANTINEOPLASTIC AGENTS	N05AE05	Lurasidone
	ANTIPSYCHOTICS	N05AH04	Quetiapine
		N05AC02	Thioridazine
		N05AG02	Pimozide
		N05	Neuroleptics
		B01AA03	Warfarin
	ANTITHROMBOTIC AGENTS	N05BE01	Buspirone
	ANXIOLYTICS	C07AB02	Metoprolol
	BETA BLOCKING AGENTS	C07AB12	Nebivolol
		C07AB02	Metoprolol

CALCIUM CHANNEL BLOCKERS	C08CA02	Felodipine
	C08CA07	Nisoldipine
CORTICOSTEROIDES	R01AD08	Fluticasone
COUGH SUPPRESSANTS	R05DA09	Dextromethorphan
DIRECT ACTING ANTIVIRALS	J05AE10	Darunavir
	J05AE02	Indinavir
	J05AR10	Lopinavir
	J05AX09	Maraviroc
	J05AE01	Saquinavir
	J05AE09	Tipranavir
	J05AG03	Efavirenz
DIURETICS	C03DA04	Eplerenone
	C03XA01	Tolvaptan
DRUGS FOR FUNCTIONAL GASTROINTESTINAL DISORDERS	A03FA02	Cisapride
HYPNOTICS AND SEDATIVES	N05CD08	Midazolam
	N05CD05	Triazolam
IMMUNOSUPPRESSANTS	L04AA18	Everolimus
	L04AA10	Sirolimus
	L04AD01	Ciclosporin
	L04AD02	Tacrolimus
INTESTINAL ANTI-INFLAMMATORY AGENTS	A07EA06	Budesonide
LIPID MODIFYING AGENTS	C10AA02	Lovastatin
	C10AA01	Simvastatin
	C10AA03	Pravastatin
OTHER ANTIHYPERTENSIVES	C02KX01	Bosentan
OTHER ANTINEOPLASTIC AGENTS	L01XE06	Dasatinib
	L01XE10	Everolimus
	L01XX33	Celecoxib
OTHER BLOOD GLUCOSE LOWERING DRUGS	A10BX02	Repaglinide
OTHER DIURETICS	C03XA02	Conivaptan
PSYCHOSTIMULANTS	N06BA09	Atomoxetine
UROLOGICALS	G04BD07	Tolterodine
	G04BD10	Darifenacin
	G04BE03	Sildenafil
	G04BE09	Vardenafil
Antibiotics/ Antiinfectives/ ANTIBACTERIALS	D06AX	Erythromycin
	D10AF	
	J01FA	

		S01AA	
	ANTIFUNGALS/ANTI- INFECTIVES AND ANTI- SEPTICS/ ANTIAD- RENAL PREPARATIONS	D01AC	Ketoconazole
		G01AF H02CA J02AB J02AC	Itraconazole
	ANTIINFECTIVES DRUGS FOR ACID RE- LATED DISORDERS	A02BA	Cimetidine
	ANTIBIOTICS/ ANTIBAC- TERIALS/ ANTIMYCO- BACTERIALS/ ANTI- INFECTIVES	D06AX	Rifampin
		J01XX J04AB J04BA S01AA	
	PSYCHOLEPTICS/ AN- TIEPILEPTICS	N03AA N05CA	Phenobarbital
	BILE AND LIVER THER- APY/ DIURETICS/ PREP- ARATIONS FOR TREAT- MENT OF WOUNDS AND ULCERS/ ANTIINFLAM- MATORY AND AN- TIRHEUMATIC PROD- UCTS/ PSYCHOLEP- TICS/ PSYCHOANALEP- TICS/ UNSPECIFIED HERBAL AND TRADI- TIONAL MEDICINE/ Ho- meopathic preparation	A05AW	HYPERICUM PER- FORATUM
		C03XW D03WX M01AW N05CM N06AW N06AX V90 V91	
Liver enzymes (ALT/AST) elevation	ANTIHYPERTENSIVES ANTIARRHYTHMICS ANTIHYPERTENSIVES ANALGESICS/ANTIEPI- LEPTICS/PSYCHOLEP- TICS MUSCLE RELAXANTS DRUGS USED IN ADDIC- TIVE DISORDERS/ AN-	C02AB C01BD C02KX N02BG N03AF N05AX M03CA N07BB P03AA	ALPHA-METHYL- DOPA AMIODARONE BOSENTAN CARBAMAZEPINE DANTROLENE DISULFIRAM

TIPARASITIC PROD- UCTS, INSECTICIDES AND REPELLENTS		
ANTIPSORIATICS/	D05BB	
ANTINEOPLASTIC	D11AX	
AGENTS	L01XF	ETRETINATE
ANTIFUNGALS/ ANTIMY- COTICS/ ANTIINFEC- TIVES	D01AC J02AC S01AX	FLUCONAZOLE
DRUGS USED IN DIABE- TES	A10BB	GLYBURIDE
ANESTHETICS	N01AB	HALOTHANE
ANTITHROMBOTIC	B01AB	
AGENTS/ VASOPRO- TECTIVES/	C05BA S01XA	HEPARIN
LIPID MODIFYING		Hmg coa reductase inhibitors
AGENTS	C10AA	ISONIAZID
ANTIMYCOBACTERIALS	J04AC	
ANTIFUNGALS/ ANTI- INFECTIVES AND ANTI- SEPTICS/ CORTICO- STEROIDS FOR SYS- TEMIC USE/ ANTIMY- COTICS	D01AC G01AF H02CA J02AB	KETOCONAZOLE
BETA BLOCKING		
AGENTS	C07AG	LABETALOL
VITAMINS/ PERIPH- ERAL VASODILATORS/	A11HA C04AC	
LIPID MODIFYING		
AGENTS	C10AD	NICOTINIC ACID
ANTIBACTERIALS	J01XE	NITROFURANTOIN
ANTIINFLAMMATORY AND ANTIRHEUMATIC PRODUCTS	M01A M01AA	NSAIDS
ANTIINFLAMMATORY AND ANTIRHEUMATIC PRODUCTS/ TOPICAL PRODUCTS FOR JOINT AND MUSCULAR PAIN	M02AA N03AB	PHENYLBUTA- ZONE
ANTIEPILEPTICS		PHENYTOIN
ANTITHYROID PREPA- RATIONS	H03BA	PROPYLTHIOURA- CIL
ANTIVIRALS	J05AE	PROTEASE INHIBI- TORS
INTESTINAL ANTIINFEC- TIVES/ ANTIBIOTICS/	A07AB D06BA	
GYNECOLOGICAL ANTI- INFECTIVES AND ANTI- SEPTICS/ ANTIBACTE- RIALS	G01AE J01EB J01EC S01AB	SULFONAMIDES
ANTIFUNGALS/ ANTI- INFECTIVES AND ANTI- SEPTICS	D01AE D01BA G01AX	
ANTIDEPRESSANTS	N06AX	TERBINAFINE TRAZODONE

QT prolongation and proarrhythmia	DRUGS USED IN DIABETES	A10BG	TROGLITAZONE
	ANALGESICS/ ANTIEPILEPTICS/ PSYCHOLEPTICS	N02CX N03AG N05AX	VALPROIC ACID
	DRUGS FOR OBSTRUCTIVE AIRWAY DISEASES/ UNSPECIFIED HERBAL AND TRADITIONAL MEDICINE	R03WA V90	EPHEDRA
	BILE AND LIVER THERAPY/ HERBAL DIGESTIVES/ UNSPECIFIED HERBAL AND TRADITIONAL MEDICINE	A05AW A09WA V90	GENTIANA LUTEA
	BILE THERAPY/ HERBAL DIGESTIVES/ ANTIGOUT PREPARATIONS/ ANALGESICS/	A09WA M04AC N02BG V90	GERMANDER SENNA ALEXANDRINA
	DRUGS FOR CONSTIPATION	A06AB V90	SCUTELLARIA
	OTHER GYNECOLOGICALS	G02CX V90	
	ANTINEOPLASTIC AGENTS/ ANTIINFLAMMATORY AND ANTIRHEUMATIC PRODUCTS	L01 M01AX	SHARK CARTILAGE
	VITAMINS	A11CA	VITAMIN A NOS ANABOLIC STEROIDS
	ANABOLIC STEROIDS	A14A A01AD N01BC	
	STOMATOLOGICAL PREPARATIONS/ ANESTHETICS	R02AD S01HA S02DA	COCAINE ECSTASY
	PSYCHOANALEPTICS	N06BA	
	ANESTHETICS/ ANALGESICS	N01AX N02BG	PHENCYCLIDINE
	Solvents and diluting agents, incl. irrigating solutions	V07AB	CARBON TETRACHLORIDE
	ANESTHETICS	N01AB	CHLOROFORM
	tertiary carboxylic acid amides	V07AY	DIMETHYLFORMAMIDUM
	ANTINEOPLASTIC AGENTS	L01XX V03AX	HYDRAZINE TRICHLOROETHYLENE
	ANESTHETICS	N01AB	
	OTHER DERMATOLOGICAL PREPARATIONS/	D11AX	
	ANTINEOPLASTIC AGENTS/	L01XX V03AX	ARSENIC

	V91	
ANTI-ACNE PREPARATIONS/ ANTIBACTERIALS/ ANTIINFECTIVES	D10AF	
IMMUNOSUPPRESSANTS/ ANTIPROTOZOALS	J01FA	
	S01AA	AZITHROMYCIN
	L04AX	
ANTIEMETICS AND ANTINAUSEANTS/ PSYCHOLEPTICS	P01BA	CHLOROQUINE
	A04AD	
ANTIBIOTICS AND CHEMOTHERAPEUTICS FOR DERMATOLOGICAL USE/ GYNECOLOGICAL ANTIINFECTIVES AND ANTISEPTICS/ ANTIBACTERIALS/ PSYCHOANALEPTICS	N05AA	CHLORPROMAZINE
PSYCHOANALEPTICS	D06AX	
PSYCHOANALEPTICS	G01AA	
ANTIEMETICS AND ANTINAUSEANTS/ PSYCHOLEPTICS	J01MA	
	S01AE	
	S03AA	
	S03AA	CIPROFLOXACIN
	N06AB	CITALOPRAM
	N06DA	DONEPEZIL
	N05AD	
	A04A	DROPERIDOL
ANTIFUNGALS FOR DERMATOLOGICAL USE/ ANTIMYCOTICS/ ANTIINFECTIVES	D01AC	
ANALGESICS/ DRUGS USED IN ADDICTIVE DISORDERS	J02AC	
	S01AX	FLUCONAZOLE
	N02AC	
	N07BC	METHADONE
ANTIEMETICS AND ANTINAUSEANTS	A04AA	ONDANSETRON
ANESTHETICS	N01AX	PROPOFOL
ANESTHETICS	N01AB	SEVOFLURANE
PSYCHOLEPTICS	N05AC	THIORIDAZINE
ANTINEOPLASTIC AGENTS	L01EX	VANDETANIB
DRUGS USED IN BENIGN PROSTATIC HYPERTROPHY		
UROLOGICALS/ ANTIPARKINSON DRUGS/ Antidotes	G04CA	ALFUZOSIN
PSYCHOLEPTICS	G04BE	
PSYCHOANALEPTICS	N04BC	
ANTIMYCOBACTERIALS	V03AB	APOMORPHINE
ANTINEOPLASTIC AGENTS	N05AH	ASENAPINE
	N06BA	ATOMOXETINE
	J04AK	BEDAQUILINE
	L01ED	CRIZOTINIB
PSYCHOLEPTICS		DEXMEDETOMIDINE
ANTIVIRALS FOR SYSTEMIC USE	N05CM	
ANTIEPILEPTICS	J05AG	EFAVIRENZ
	N03AX	FELBAMATE
	A12CX	
	D11AX	LITHIUM

MINERAL SUPPLE-	N05AN	
MENTS/ PSYCHOLEP-		
TICS	V04CX	
CALCIUM CHANNEL		
BLOCKERS	C08CA	NICARDIPINE
ANTIHYPERTENSIVES/	C02KX	
UROLOGICALS	G04BE	VARDENAFIL
ANTINEOPLASTIC		
AGENTS	L01EC	VEMURAFENIB
ANALGESICS/ PSYCHO-	N02CX	
LEPTICS/ ANXIOLYTICS/	N05BX	
ANTIDEPRESSANTS	N06AX	VENLAFAXINE
ANTINEOPLASTIC		
AGENTS	L01XH	VORINOSTAT

Note: Use ATC Code (4th level code - ATC4) and Preferred term (CMDECOD) for merging to get information about medications as we do not have 5th level code (ATC5) information in the database.

